4.7.1.3 Reporting of serious adverse events

The Investigator and other site personnel must inform appropriate AstraZeneca representatives of any SAE that occurs in the course of the study within 1 day (ie, immediately but no later than the end of the next business day) of when he or she becomes aware of it.

The AstraZeneca representative will work with the Investigator to compile all the necessary information including the Investigator’s causality assessment, and ensure that the appropriate AstraZeneca Drug Safety Department receives a report by day one for all fatal and life-threatening cases and by Day 5 for all other SAEs.

Follow-up information on SAEs must also be reported by the Investigator within the same time frames.

If a non-serious AE becomes serious, this and other relevant follow-up information must also be provided to AstraZeneca within one day as described above. For a non-serious AE that become serious but which is not fatal or life-threatening a report should be received within 5 days.

All SAEs have to be reported, whether or not considered causally related to the investigational product or to the study procedure(s). All SAEs will be recorded in the CRF. The Investigator and/or Sponsor are responsible for informing the Ethics Committee and/or the Regulatory

Authority of the SAE as per local requirements. For studies in countries implementing the EU Clinical Trials Directive, this will be taken care of by AstraZeneca (see Section 7.1).

5. STUDY MANAGEMENT

5.1 Monitoring

5.1.1 Study monitoring

The monitoring of this study will be performed in accordance with the principles of GCP as laid out in the International Conference on Harmonization (ICH) document “Good Clinical Practice: Consolidated Guideline”.

The specific requirements of the genetic part of the study will be discussed with the Investigator (and other personnel involved with the study).

5.1.2 Data verification

It is a prerequisite of this study that the study monitor has direct access to source data for data verification. This will be done by comparing data from the CRFs with those in the volunteer’s medical notes (permission from the volunteer will be sought as part of the consent process). Such verification is an essential element of quality control, as it allows the rectification of transcription errors and omissions.

For this study original data recorded on the CRF and regarded as source data are as follows:

- Blood pressure, pulse, height and weight at Visit 1b (and all at Visit 5, except height and weight which are not captured).
- Adverse events.
- Concomitant medication.

Monitoring including source data verification should routinely be performed prior to the transfer of data to Data Management.

Source verification of the genetic consent of participating volunteers will be performed to make sure that the investigational team is adhering to the specific requirements of the genetics aspects of the study.

5.2 Audits and inspections

Authorised representatives of AstraZeneca, a regulatory authority, and an Ethics Committee may visit the centre to perform audits or inspections, including source data verification. The purpose of an AstraZeneca audit or inspection is to systematically and independently examine all study-related activities and documents to determine whether these activities were conducted, and data were recorded, analysed, and accurately reported according to the

protocol, GCP guidelines of the ICH and any applicable regulatory requirements. The Investigator should contact AstraZeneca immediately if contacted by a regulatory agency about an inspection at his or her centre.

5.3 Training of staff

The Principal Investigator will maintain a record of all individuals involved in the study (medical, nursing and other staff). He or she will ensure that appropriate training relevant to the study is given to all of these staff, and that any new information of relevance to the performance of this study is forwarded to the staff involved.

Before the first volunteer is entered into the study the investigational staff will have an opportunity to discuss the procedures associated with the collection of blood samples, extraction of DNA and genetic testing with AstraZeneca personnel. The ethical considerations specific to genotyping and the importance of the informed consent process will be made clear. The requirements for the collections of the volunteers' samples will also be made clear.

5.4 Changes to the protocol

Study procedures will not be changed without the mutual agreement of the Principal Investigator and AstraZeneca.

If it is necessary for the study protocol to be amended, the amendment and/or a new version of the study protocol must be notified to or approved by each Ethics Committee, and in many countries also the local regulatory authority, before implementation. Local requirements must be followed.

If an administrative change is required, such a change must be notified to or approved by each Ethics Committee according to local requirements.

If a protocol amendment requires a change to a particular centre's Informed Consent Form, then AstraZeneca and the centre's Ethics Committee must be notified. Approval of the revised Master Informed Consent Form by AstraZeneca and by the Ethics Committee is required before the revised form is used.

[REDACTED] will distribute amendments and new versions of the protocol to the Investigator who in turn is responsible for the distribution of these documents to his or her Ethics Committee, and to the staff at his or her centre. The distribution of these documents to the regulatory authority will be handled according to local practice.

5.5 Study agreements

The Principal Investigator must comply with all the terms, conditions, and obligations of the study agreement for this study. In the event of any inconsistency between this protocol and the study agreement, this protocol shall prevail.

5.6 Study timetable and end of study

The study is expected to start in [REDACTED] and to be completed by [REDACTED].

5.7 Data management

5.7.1 Case report forms

Paper CRFs (pCRFs) will be used to record all data not captured electronically. Data should be recorded legibly onto the pCRFs in blue or black ballpoint pen. Correction fluid or covering labels must not be used.

The Study Monitor will check data at the monitoring visits to the study site. The Investigator will ensure that the data in the pCRFs are accurate, complete and legible.

Data from the completed pCRFs will be entered (double data entry) onto the clinical study database and validated under the direction of the Data Manager. Any missing, impossible or inconsistent recordings in the pCRFs will be identified by electronic edit checks during data validation, and will be referred back to the Investigator using a data query form and documented for each individual volunteer until the database is declared clean prior to Quality Control checks and the final Database Lock.

5.7.2 Genetic data

In the case of genotypic data, only the date the volunteer gave consent to participation in the genetic research and the date the blood sample was taken from the volunteer will be recorded in the pCRF and database.

The genotypic data generated from the study will be stored in the AstraZeneca LIMS database or other appropriate system. This database is a secure database, which is separate from the database used for the main study. Some or all of the datasets from the main study may be duplicated within the AstraZeneca LIMS database for exploratory genetic analysis.

5.8 Reporting of genotypic results

Results from any genetic research performed will be reported separately from the CSR. AstraZeneca will not provide individual genotype results to volunteers, their family members, any insurance company, an employer, clinical study Investigator, general physician or any other third party, unless required to do so by law. The volunteer's DNA will not be used for any purpose other than those described in the study protocol.

Individual volunteers will not be identified in any report or publication resulting from this work. The data and results of this study may be reviewed with collaborators and published, but neither the volunteer's name nor any other personal identifiers will appear in any publication or report.

6. PHARMACOKINETIC, PHARMACODYNAMIC, SAFETY, GENETIC AND STATISTICAL METHODOLOGY

6.1 Pharmacokinetic / pharmacodynamic evaluation

6.1.1 Calculation or derivation of pharmacokinetic variables

The pharmacokinetic analyses will be performed by [REDACTED]

6.1.1.1 Single dosing

The PK parameters will be calculated using non-compartmental analysis. The PK parameters measured at Day 1 and Day 7 include:

Maximum plasma drug concentration (C_{max}), time to maximum plasma drug concentration (t_{max}), area under the (plasma drug concentration-time) curve from time zero to time t ($AUC_{(0-t)}$), area under the (plasma drug concentration-time) curve from time zero to infinity (AUC), AUC from time zero to 12 hours ($AUC_{(0-12)}$), AUC from time zero to 24 hours ($AUC_{(0-24)}$), terminal half-life of drug in plasma ($t_{1/2}$), apparent terminal volume of distribution following oral drug administration (Vz/F), apparent plasma clearance following oral drug administration (CL/F), renal clearance (CL_R), cumulative amount excreted in urine (A_e), and fraction of dose excreted unchanged in the urine (F_e).

6.1.1.2 Multiple dosing

Day 13: C_{max} ; t_{max} ; $AUC_{(0-12)}$; concentration at 12 hours post dose (C_{12}); A_e ; F_e . The A_e and F_e will be estimated using data from 0-12 hours

Day 19: Minimum plasma (trough) drug concentration after repetitive dosing after steady state is achieved, prior to the first dose of the study day ($C_{min,ss}$), C_{max} at steady state ($C_{max,ss}$), t_{max} at steady state ($t_{max,ss}$), $AUC_{(0-12)}$ at steady state ($AUC_{(0-12),ss}$), $AUC_{(0-24)}$ at steady state ($AUC_{(0-24),ss}$), AUC at steady state (AUC_{ss}), Vz/F at steady state (Vz/F_{ss}), CL/F at steady state (CL/F_{ss}), $t_{1/2}$ at steady state ($t_{1/2,ss}$), CL_R , A_e at steady state ($A_{e,ss}$), F_e at steady state ($F_{e,ss}$), accumulation ration (R_{ac}), C_{12} at steady state ($C_{12,ss}$)

The R_{ac} will be calculated using the following equation:

$$R_{ac} = AUC_{(0-12),ss} \text{ Day 19} / AUC_{(0-12)} \text{ Day 13}$$

6.1.2 Calculation or derivation of pharmacodynamic variables

The inhibition of the post-dose zymosan stimulated NE activity will be derived using the following formula:

$$100 - ((\text{post dose stimulated NE activity} - \text{post dose unstimulated NE activity}) / (\text{pre dose Day 1 stimulated NE activity} - \text{pre dose Day 1 unstimulated NE activity})) * 100$$

6.1.3 Calculation or derivation of pharmacokinetics/pharmacodynamics

The relationship between AZD9668, and the effect of dose on the *ex vivo* zymosan stimulated NE activity in plasma will be explored graphically.

6.2 Safety evaluation

6.2.1 Calculation or derivation of safety variables

Adverse events will be analysed by means of descriptive statistics and qualitative analysis, AEs will be listed for each volunteer and summarised by System Organ Class and Preferred Term assigned to event by using MedDRA (Version 10 or higher).

Concomitant medications will be classified according to the AZDD Drug Dictionary, the ATC system and the CPMP route of administration dictionary. All concomitant medications reported at entry and recorded during the study will be listed.

Abnormalities in laboratory safety data, vital signs, ECG or physical examination will only be reported as AEs if they are accompanied by clinical symptoms, constitute SAEs or lead to discontinuation of treatment with the investigational product. For the laboratory safety data, vital signs, and ECG data change from pre dose Visit 2 will be calculated.

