3. STUDY PLAN AND PROCEDURES

3.1 Overall study design

This Clinical Study Protocol has been subjected to a peer review according to AstraZeneca standard procedures.

This is double blind, randomised, placebo controlled, parallel group, Phase 1 study. Up to four single dose levels, and two multiple dose levels will be studied in two Japanese and two Caucasian cohorts, each comprising of eight healthy volunteers: In each cohort, two single dose levels, and one multiple dose level will be studied, each separated by a washout period (minimum of 7 days), with the intention that parallel cohorts of Japanese and Caucasian healthy volunteers (age and sex matched) are studied concurrently.

Each volunteer will receive two ascending single doses once daily (on Days 1 and 7), followed by multiple doses (twice daily each dose administered 12 hours apart) for 6 days (Days 13-18), and a final single dose on the morning of Day 19 (ie, a total of 15 doses).

Cohorts of Japanese and Caucasian volunteer will receive the same dose of AZD9668, and will be run in parallel as far as is possible.

The intention is that volunteers remain resident in the [REDACTED] from Day -1 until approximately 72 hours after each of the single doses and after the last dose in Visit 4 (ie, from Day -1 to Day 4; Day 6 to Day 10; and Day 12 to Day 22). The volunteers will be allowed home in between the single doses or may stay in the unit at the Investigators discretion. If the dosing schedule is separated further for practical reasons, volunteers will be allowed home, from approximately 72 hours after the last dose in each treatment period. (Note - Further separation of the dosing periods will not affect the 'study day' nomenclature).

Figure 1 shows the study flow chart and Table 1 outlines the assessments at each visit.

Visit 1a (to provide informed consent only) and Visit 1b (enrolment and screening) will take place up to 21 days prior to Visit 2.

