⁷ Telemetry from -1 to 24 hrs post-dose at Visits 2, 3 and 4, and from -1 to 24 hrs post dose on Day 19 (Visit 4).

⁸ Vital signs will be measured at the timepoints shown in Table 2.

⁹ Female volunteers only.

¹⁰ PK sampling times are detailed in Table 3.

¹¹ Urine collections: Pre-dose on Days 1, 7 and 13 and post dose at 0-4, 4-8, 8-12, 12-24, 24-36, 36-48 hrs on Days 1, 7 and 19. On Day 13 at 0-4, 4-8, 8-12 hrs post dose.

¹² Pharmacodynamic (PD) blood sampling times are shown in Table 4.

¹³ Pharmacogenetic (PGx) blood sample to be obtained at any suitable timepoint post dose.

Table 2 ECG and vital signs assessment schedule – Visits 2, 3 and 4

Time (Relative to dosing)
-01:00
00:00
00:30
01:00
01:30
02:00
03:00
04:00
06:00
08:00
12:00
24:00

Paper ECGs, dECGs (if required), and vital signs (ie, sitting blood pressure and pulse) will be performed at the above times at Visits 2 and 3 (single doses) and after the first and last multiple doses (ie on Days 13 and 19 [Visit 4]). Paper ECGs will also be measured at 48 and 72 hours post dose at Visits 2, 3 and 4.

Table 3 Pharmacokinetic sampling schedule

Day	Time (hours - relative to dosing)
1	Pre-dose, 0.25, 0.5, 1, 2, 3, 4, 5, 7, 9, 12, 24, 36, 48, 72 post-dose
7	Pre-dose, 0.25, 0.5, 1, 2, 3, 4, 5, 7, 9, 12, 24, 36, 48, 72 post-dose
13	Pre-dose, 0.25, 0.5, 1, 2, 3, 4, 5, 7, 9, 12 (pre-dose 2), 13, 15 post-dose
14 and 15	Pre-dose (dose 1)
16 and 17	Pre-dose (dose 1), 1 post-dose
18	Pre-dose (dose 1)
19	Pre-dose, 0.25, 0.5, 1, 2, 3, 4, 5, 7, 9, 12, 24, 36, 48, 72 post-dose

Table 4 Pharmacodynamic sampling schedule

Day	Time (hours - relative to dosing)	
	Cohort 1	Cohort 2
1	Pre-dose, 1, 24 post-dose	Pre-dose, 1, 48 post-dose
7	Pre-dose, 1, 48 post-dose	Pre-dose, 1, 48 post-dose
13	Pre-dose (dose 1), 1 post-dose	Pre-dose (dose 1), 1 post-dose

Time (hours - relative to dosing)		
19	Pre-dose, 1, 24 post-dose	Pre-dose, 1, 48 post-dose

Total of 11 blood samples per volunteer in each cohort.

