The proposed single dose levels are 30 mg, 60 mg, 120 mg and 150 mg, although they may change with emerging data from this study. The top dose will be no higher than 150 mg as this is the maximum dose that was administered to healthy volunteers in the AstraZeneca Global SAD/MAD Study and was found to be safe. In addition, modelled PK data from the current study will ensure that the predicted geometric mean C_{max} and $AUC_{(0-24)}$ at the top dose will not exceed 2.5 μM or 18 $\mu\text{M}\cdot\text{h}$, respectively. The multiple doses for both cohorts 1 and 2 will be selected following a safety review meetings using emerging data from the current study and the AstraZeneca Global SAD/MAD Study. The maximum multiple dose will be capped at a total daily dose of 140 mg. In addition, the emerging PK data from the current study will be modelled to ensure that for the highest dose given, the predicted geometric mean exposures (both $AUC_{(0-24),ss}$ and $C_{max,ss}$) will not exceed 2.5 μM or 18 $\mu\text{M}\cdot\text{h}$, respectively.

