3.2 Rationale and risk/benefit assessment

3.2.1 Rationale for study design, doses and control groups

A first administration to man, Phase I, randomised, double blind, placebo controlled, two-part AstraZeneca Global SAD/MAD Study to assess the safety and tolerability and PK of single and multiple oral doses of AZD9668 in healthy volunteers is ongoing. Up to [REDACTED], AZD9668 has been administered in single ascending doses of 2 mg, 10 mg, 30 mg, 60 mg, 120 mg and 150 mg with 36 subjects receiving the active drug and 12 subjects receiving the placebo. No serious adverse events (SAEs) occurred. There were 46 non-serious adverse events (AEs) reported by 24 subjects. The severity for the majority of the events was mild (37/46 AEs); few were reported as moderate (7/46 AEs), and for one subject, two events were reported as severe (syncope associated with a symptomatic

bradycardia, 4 hours 37 minutes after a 2 mg dose). These last two events resolved with supportive care within 3 minutes. The most frequently reported AE was headache (18/10 subjects), followed by musculo-skeletal pain/myalgia/backpain (5/4 subjects) and light headedness (3/2 subjects). None of the AEs were considered by the Investigator to be causally related to the investigational drug. The multiple ascending dose part of this study has commenced on the [REDACTED], at 30 mg daily for 8 days, with no safety or tolerability issues identified so far.

The present study will be conducted in healthy volunteers, in a double blind, placebo controlled manner, and volunteers will be randomised to receive either AZD9668 or placebo

Healthy volunteers will be used in this study in order to optimise compliance with study procedures and to avoid interference with the results from disease processes and other drugs. The inclusion/exclusion criteria are defined such that the volunteers selected will be known to be free of any significant illness when included in the study. This study is being performed double blind in order to minimise both potential selection bias in the allocation of volunteers to specific treatments and bias to the volunteer's data as a result of the volunteer or study personnel being aware of whether a volunteer is receiving AZD9668 or placebo. The placebo control will provide a reference to aid interpretation of safety and tolerability data.

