3.4.3 Method of assigning subjects to treatment groups

Informed consent will be obtained before enrolment and the volunteers identified with an enrolment number starting with E0001001. Numbers will be allocated in ascending order.

Volunteers fulfilling the eligibility criteria will be assigned randomisation codes (unique volunteer numbers), starting with 100 (Japanese volunteers) and 200 (Caucasian volunteers). Numbers will be allocated in ascending order.

Volunteers will be assigned randomisation codes strictly sequentially as volunteers are eligible for randomisation. If a volunteer discontinues from the study the volunteer number will not be re-used and the volunteer will not be allowed to re-enter the study.

The randomisation schedule and associated individual treatment code envelopes (emergency unblinding tools) giving details of individual volunteer treatment will be produced by computer software (SAS[®]) that incorporates a standard procedure from generating randomisation codes.

Both Japanese and Caucasian volunteers will be allocated to either AZD9668 or placebo in a 6:2 ratio (AZD9668:placebo) per cohort. At each dose level, Japanese and Caucasian volunteers will be gender and age matched (± 5 years).

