6.4.4 Methods of statistical analyses

Data will be summarised by dose administered using descriptive statistics and graphical output. In addition due to the exploratory nature of the study other statistical methods may be used where appropriate.

Summary statistics will be presented for continuous variables, by way of n, mean, standard deviation (SD), median, minimum and maximum and by way of group frequencies and percentages for categories of categorical variables. Percentages will be calculated using the total volunteers per treatment group. In addition, geometric mean, geometric coefficient of variation (CV%) and 95% confidence intervals will be presented for the PK concentrations and parameters.

No formal analysis testing is planned.

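### Vital-sign and ECG changes at Visits 3 and 4 are measured only from Visit 2, although pre-dose readings on Days 7 and 13 are already scheduled

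*Protocol*

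**What the plan says.** Protocol Section 6.2.1 defines the change variable in one sentence: "For the laboratory safety data, vital signs, and ECG data change from pre dose Visit 2 will be calculated". It gives no other baseline for Visits 3 or 4. It also does not say which of the Visit 2 pre-dose readings is meant, or whether they are averaged.

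Table 2 (Section 3.1) lists twelve times for ECG and vital signs, starting at -01:00 and 00:00 relative to dosing. The note below it says that these assessments "will be performed at the above times at Visits 2 and 3 (single doses) and after the first and last multiple doses", that is, on Days 1, 7, 13 and 19.

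On dosing, Section 3.1 says "Each volunteer will receive two ascending single doses once daily (on Days 1 and 7"; twice-daily dosing follows on Days 13 to 18, with a last dose on Day 19. It also says "The proposed single dose levels are 30 mg, 60 mg, 120 mg and 150 mg", with two single levels per cohort. The periods may be further apart than the day numbers suggest ("If the dosing schedule is separated further for practical reasons"), because the study-day labels do not change when that happens.

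Section 3.4.3 has volunteers "allocated to either AZD9668 or placebo in a 6:2 ratio (AZD9668:placebo) per cohort" in each ethnic group. Section 3.2.1 gives the role of that arm: "The placebo control will provide a reference to aid interpretation of safety and tolerability data". Section 6.4.4 says "Data will be summarised by dose administered using descriptive statistics and graphical output" and does not mention period.

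**The concern.** The synopsis lists ECG, blood pressure and pulse among the safety variables and makes safety a primary variable. For an acute effect, the informative comparison is before and after the dose within one period. With the Visit 2 baseline, a change on Day 7 mixes the response to that day's dose with whatever else has shifted since Day 1. Volunteers may have gone home in between, they have become used to the unit, and blood sampling has accumulated. Every volunteer meets the doses in the same sequence, so in a cohort's active arm that shift coincides with the move to the next dose or regimen. A small acute effect could be blurred or imitated, although readings that would remove much of the shift are already collected.

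Laboratory data are outside this point. The footnote to Table 1 has safety samples taken pre-dose in each dosing period, so there is no within-period change to calculate.

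**Working it through.** The protocol states no figure to reproduce: there is no powering and no SD for ECG or vital signs. The check has four parts.

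**1. Time between baseline and measurement** (nominal days, Section 3.1 and Table 2).

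| Measured on | From Visit 2 | From same-period pre-dose |
|---|---|---|
| Day 1 | 0 | 0 |
| Day 7 | 7 - 1 = 6 | 0 |
| Day 13 | 13 - 1 = 12 | 0 |
| Day 19 | 19 - 1 = 18 | 19 - 13 = 6 |

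Day 19 pre-dose is an on-treatment trough, so the period baseline for Visit 4 is Day 13.

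**2. Lag by dose.** Cohort 1 starts at 30 mg (Section 3.2.1). With the proposed levels taken two per cohort, 30, 60, 120 and 150 mg fall on Days 1, 7, 1 and 7. The lags are 0, 6, 0 and 6 days.

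**3. Can drift be separated from dose?** Model the cell means with an intercept, a drift term for each of periods 2 and 3 (common to cohorts and arms), and one effect for each of the six active cells (2 cohorts x 3 periods). That is 1 + 2 + 6 = 9 parameters.
- Active arm alone: 6 cells, rank 6 of 9. Drift and dose cannot be separated.
- With placebo kept by period: 12 cells, rank 9 of 9. Drift is estimable and cancels on average in active minus placebo within a period.

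**4. Noise.** Let a reading be the sum of a volunteer effect, a day effect (SD s_d) and a reading error (SD s_w). Take the baseline as the mean of the -01:00 and 00:00 readings, treating 00:00 as taken just before dosing.
- Change from Visit 2, measured on Day 7 or 13: variance = s_w²(1 + 1/2) + 2s_d².
- Change from the same day's baseline: variance = 1.5s_w².

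The ratio s_d/s_w is an assumption:

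| s_d/s_w | Variance ratio | SD ratio |
|---|---|---|
| 0 | 1.5/1.5 = 1.00 | 1.00 |
| 0.5 | (1.5 + 0.5)/1.5 = 1.33 | 1.15 |
| 1.0 | (1.5 + 2)/1.5 = 2.33 | 1.53 |

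For Day 19 the Day 13 baseline is still a different day. If day effects are independent, the variance does not fall; the gain is only a drift window of 6 days in place of 18.

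At s_d = s_w = 1, a Visit 2 change has SD √3.5 = 1.87 and a same-day change has SD √1.5 = 1.22. In units of s_w:
- SE of drift estimated from placebo: 1.87/√2 = 1.32 with 2 volunteers; 1.87/√4 = 0.94 with 4.
- SE of active minus placebo, 6 against 2: multiply by √(1/6 + 1/2) = 0.816. This gives 1.53 from Visit 2 and 1.00 from the same day.
- SE of active minus placebo, 12 against 4 (ethnic groups pooled): multiply by √(1/12 + 1/4) = 0.577. This gives 1.08 and 0.71.

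Subtracting placebo removes drift on average but leaves the extra noise in place.

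**The case against.** **Visit 2 is a sound baseline.** It is the only drug-naive one, it shows carry-over and cumulative effect, and the pharmacodynamic formula in Section 6.1.2 also uses pre-dose Day 1. This stands in full. A period baseline would absorb carry-over, so it should be added and not substituted.

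**Placebo deals with drift.** Placebo volunteers pass through the same periods, so drift is separable. This stands in principle. In practice it rests on 2 to 4 volunteers and needs placebo tabulated by period.

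**The analysis plan could add this.** Section 6.2.1 does not say that no other change may be calculated, Section 6.4.4 leaves room for other methods, and Section 6.6 leaves data presentation to the analysis plan, which is not at hand. This is why the point is small. Still, the sentence in 6.2.1 is the one rule that the protocol states, and it passes over readings that the protocol itself schedules.

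**No escalation decision is shown to turn on these tables.** Section 3.1.1 works through individual thresholds and committee review. This also stands.

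A reader might infer that drift rises with dose throughout. It does not: the lags for the four proposed single doses are 0, 6, 0 and 6 days. In cohort 2 the multiple dose, capped at 140 mg per day, would follow a single dose of 150 mg, so the longest lags do not go with the highest dose. A reader might also infer that drift and dose are inseparable in the trial as a whole; that is true only of the active arm read alone.

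**Conclusion.** The point holds as a minor improvement. Change from pre-dose Visit 2 is the only change variable stated for vital signs and ECG. On Days 7, 13 and 19 it includes a nominal 6, 12 and 18 days of between-period variation, or more if periods are separated further. Visit 2 is unaffected.

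The extra SD on Days 7 and 13 is between nothing and 53%. That range rests on an assumed between-day SD of 0 to 1.0 times the within-day SD and on averaging two pre-dose readings; the protocol supplies neither. The direction is less dependent on assumptions: any between-day variance makes the Visit 2 change noisier on those two days. For Day 19 the benefit is a shorter drift window only.

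The documents do not support calling the Visit 2 baseline wrong, or claiming that a dose trend will be created or hidden. They give no figure for the size of any drift, and the study is descriptive with no hypothesis tested.

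**What to change.** In Section 6.2.1, keep change from pre-dose Visit 2 for laboratory data, vital signs and ECG. For vital signs and ECG, add change from the mean of the -01:00 and 00:00 readings of the same period: Day 7 pre-dose for Visit 3, and Day 13 pre-dose for both Day 13 and Day 19. Say in the same sentence whether the Visit 2 baseline is also the mean of its two readings.

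Tabulate the period baselines themselves, and state in Section 6.4.4 that placebo is shown by period.

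The cost is a short addition to the text and one extra set of tables, with no new measurements. The drawback is that the period baseline hides any carry-over from an earlier dose; the retained Visit 2 change and the tabulated baselines keep it visible.
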